9 ETHICAL CONSIDERATIONS

9.1 Regulation statement

This study will be conducted according to the principles of the declaration of Helsinki (Brasil, 2013) and in accordance with the Medical Research Involving Human Subjects Act (WMO).

9.2 Recruitment and consent

Patients are recruited from a specialised centre for bipolar disorders in psychiatric hospital (Centrum Bipolair GGzE). The lead clinician (regie behandelaar) identifies eligible patients and subsequently give these patients the information letter as well as oral information about the study and asks permission to hand over their contact information to the researcher should they consider participating. Once patients have indicated to their nurse, psychiatrist or psychologist they would like to participate in this study, the researcher makes an appointment with the patient. During this appointment the researcher answers any remaining questions and if patients still agree with participation in the study they are given the informed consent letter. After one week in which patients can consider their participation in this study, the researcher makes another appointment with the participant during which both the researcher and participant sign the informed consent letter. At all times can patients withdraw from the study without explanation. Moreover, they have the opportunity to consult an independent expert (dr. [name]). Note that during the whole time that patients participate in this study they are allowed to continue or start with advice on mood stabilising medication from their psychiatrist.

Once the researcher has obtained informed consent, baseline measures are administered. Patients start with four weeks daily mood measurements. At the end of these four weeks, they are randomly allocated to either ImCt or psychoeducation treatment condition and fill in the pre-intervention measurements online after which they start with either of both treatments. At the end of the treatments they fill in the post-intervention measurements online. At 8 and 16 weeks follow-up measurements the patients fill in measurements online. All patients continue their daily mood monitoring until follow-up at 16 weeks. Screening for eligibility ceases after 96 patients are included, 48 in each condition.

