4.2 Inclusion criteria

In order to be eligible to participate in this study, a subject must meet all of the following criteria:

- Aged 18-68
- Sufficient Dutch language ability to permit the assessment to be completed.
- Diagnosis of BD (I or II or unspecified) according to DSM-5 (clinicians assessment).
- Willing to complete daily and weekly monitoring throughout the duration of the study.
- Successful completion of the daily monitoring in the 4 weeks active run-in phase.
- Willing to be randomised to either ImCT or psychoeducation condition
- Able to attending 12 consecutive weekly sessions ImCT or 6 weekly two hours sessions psychoeducation/TAU.

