6. METHODS

6.1 Study parameters/endpoints

6.1.1 Main study parameter/endpoint

To assess the primary endpoint of this study (1), decrease of mood variability, mood variability is measured using the Affect Lability Score Short Version (ALS-18) (Oliver & Simons, 2004) at baseline (T0), pre- intervention (T1) and post intervention (T2), and at follow-up measurements at 8 (T3) and 16 weeks (T4) after treatment discontinuation in both the ImCT and psychoeducation conditions. The ALS-18 is a self-report scale measuring lability in affect and consists of 18 items. Ratings are made on a 4-point scale with a maximum score of 72. Scores range from A= very characteristic of me (4 points), to D= very uncharacteristic of me (1 point).

In addition we monitor changes in mood variability using the National Institute of Mental Health Life Chart Methodology (NIMH-LCM) Prospective Self-Rating (Denicoff et al., 2000). Participants rate their mood (both mania and depression) on a 9-point Likert scale, ranging from -4 (severe depression, admission required due to severe dysfunction) to 0 (stable mood) to +4 (severe mania, admission required due to severe dysfunction). Daily measurements are calculated during a 4-week baseline prior to start of either ImCT or psychoeducation, during the intervention and until follow up at 16 weeks. This method is advised given that traditional self-report mood ratings over a single time point are scarcely representative of mood variability in bipolar disorder.

6.1.2 Secondary study parameters/endpoints (if applicable):

The following parameters are used for the following secondary objectives:

To assess (2a) level of depression, mania and anxiety and (2b) general functioning and hopelessness (3) number of relapses into mania or depression decline/increase, we administer the following measures:

- Level of depression, using the Quick Inventory of Depressive Symptoms (QIDS-SR) (Rush et al., 2003). The QIDS-SR is a 16-item self-report rating scale in which the nine DSM 5 symptoms of major depression are incorporated. Answers are rated on a four-point Likert scale (0-3). The QIDS-SR is administered weekly throughout the duration of the study.

- Level of mania, using the Altman Self-Rating Mania Scale (ASRM-NL) (Altman, Hedekker, & Peterson, 1997). The ASRM-NL is a 5 item self-report instrument to measure severity of mania symptoms. This is administered weekly throughout the duration of the study.

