6.2 Randomisation, blinding and treatment allocation

An independent central research assistant will randomize participants to treatment condition (ImCT or psychoeducation) after checking all in- and exclusion criteria. Randomization will be based on block randomization with (N=10) per block to guarantee a balance between conditions over time and stratified for mood stabilising medication (either mood stabilising medication, or no mood stabilising medication), so that mood stabilising medication is controlled per arm. Stratification for mood stabilising medication is necessary because not using mood stabilizing medication can seriously affect the primary outcome variable. We roughly estimate that 15 percent of the participants in GGzE will have no mood stabilising medication, but there are no firm data available. Blinding of participants and therapists to treatment condition is not possible in this kind of psychotherapy trial, but the assessments will be blind to treatment condition as they are filled in online.

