6.3.2 Study Assessment Moments

Psychoeducation groups at Centrum Bipolar start once in every six weeks. At four weeks prior to the start of each psychoeducation group the identified participants start with the online measures at baseline (T0), and both daily and weekly online measurements which participants receive by email. Note here that the patients that participate in this study will not wait longer than the patients that choose not to participate. Participants continue to fill in both the daily and weekly online measures for four weeks (the baseline period). After four weeks all participants fill in the measures pre-intervention (T1), and are allocated randomly to either the ImCT or psychoeducation condition, which will then commence. During the intervention period (12 weeks for the ImCT condition, and 6 weeks for the psychoeducation treatment condition) all participants continue to fill in both the daily and weekly online measures. At the end of the intervention, all participants fill in the post-intervention measures (T2) online. Subsequently, all participants continue to fill in both daily and weekly online measures until the end of the study (at follow up at 16 weeks). In addition, participants fill in the post-intervention online measures at follow up at 8 weeks (T3) and 16 weeks (T4) after the end of intervention.

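### Sections 6.3.2 and 9.2 list T1 and allocation in opposite order, so one of the five ALS-18 scores in the primary analysis may be self-rated with the arm known

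*Combined protocol and SAP*

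**What the plan says.** Section 6.3.2 (Study Assessment Moments) describes the end of the run-in as follows: "After four weeks all participants fill in the measures pre-intervention (T1), and are allocated randomly to either the ImCT or psychoeducation condition", after which treatment begins. Section 9.2 (Recruitment and consent) describes the same moment the other way round: "they are randomly allocated to either ImCt or psychoeducation treatment condition and fill in the pre-intervention measurements online", and then treatment begins. Section 6.1.1 lists the ALS-18 time points as "at baseline (T0), pre- intervention (T1) and post intervention (T2"), followed by the two follow-ups, so the pre-intervention measures of section 9.2 are T1.

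Two other sections bear on the timing but do not settle it. Section 6.2 says only that randomisation happens "after checking all in- and exclusion criteria". Section 4.2 makes "Successful completion of the daily monitoring in the 4 weeks active run-in phase" an eligibility criterion, which places randomisation at about the time of T1 but neither before nor after it.

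On blinding, section 6.2 states that "Blinding of participants and therapists to treatment condition is not possible in this kind of psychotherapy trial", and adds that "the assessments will be blind to treatment condition as they are filled in online". Section 8 enters the ALS-18 at T0, T1, T2, T3 and T4 as the repeated dependent scores of the primary analysis, with treatment condition as the between-subjects factor.

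**The concern.** A score taken before randomisation can differ between arms only by chance. A score taken after patients learn their arm can also carry hope or disappointment about the allocation. The arms are easy to tell apart here: individual weekly ImCT sessions over 12 weeks, or group psychoeducation over 6 weeks. Completing the form online does not make it blind, because the rater is the patient.

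T1 is the last measurement before treatment, and the primary hypothesis is about differential decrease. If T1 shifts in one arm because of the allocation, the profile of the five scores differs between arms without any treatment effect, and any contrast that takes T1 as its starting point inherits the shift. The functioning, hopelessness and imagery questionnaires follow the same T0 to T4 schedule and have the same exposure.

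**Working it through.** **Order of steps.**

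| Section | Listed first | Listed second | Then |
|---|---|---|---|
| 6.3.2 | T1 measures | Allocation | Treatment starts |
| 9.2 | Allocation | Pre-intervention measures (T1) | Treatment starts |
| 6.2 with 4.2 | Eligibility check, including run-in completion | Randomisation | Place of T1 not stated |

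The only strict order that both descriptions share is that treatment comes last. Neither says when the patient is told the arm.

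**The plan's own sample size (section 4.4).** With d = 0.6, two-sided alpha 0.05 and 80% power, a two-sample t-test needs 44.6, rounded up to 45 per arm (power at 45: 80.4%). Dropout of 1 in 15 gives 45 × (1 + 1/15) = 48. The stated 45 and 48 reproduce. The order of T1 and allocation does not affect them.

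**Illustration of size.** The protocol gives no figure for a reaction to allocation and no correlation between time points, so both are assumed:
- n = 45 per arm (section 4.4).
- Correlation 0.6 between all pairs of time points, common SD of 1.
- No true treatment effect.
- T1 shifted by s SD in one arm only, with s = 0.1, 0.2 or 0.3. With the pilot pre-treatment SD of 11.26 (Table 1), s × 11.26 is 1.1, 2.3 or 3.4 ALS-18 points.

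*Omnibus group-by-time test on T0 to T4.* A shift at one of five times leaves a centred sum of squares of s² × (1 − 1/5) = 0.8s². The within-patient variance is 1 − 0.6 = 0.4. The noncentrality is (45/2) × 0.8s²/0.4 = 45s², that is 0.45, 1.80 and 4.05. Against the multivariate F on 4 and 85 degrees of freedom, the rejection rates are 7.2%, 15.1% and 30.7%. A simulation of 4,000 runs under the same assumptions gave 7.3%, 15.5% and 32.2%.

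*Contrasts with and without T1* (the first row is analytic; the other three are from the same simulation):

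| Comparison | s = 0.1 | s = 0.2 | s = 0.3 |
|---|---|---|---|
| T2 minus T1 change, SD √(2 × 0.4) = 0.894 | 8.2% | 18.2% | 35.0% |
| T2 minus T0 change | 4.7% | 5.3% | 5.0% |
| Between-arm t-test at T2 | 4.9% | 5.3% | 5.1% |
| Significant omnibus and any Bonferroni-corrected between-arm t-test at T2 to T4 | 0.8% | 1.5% | 2.3% |

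The middle two rows stay at the nominal 5% within simulation error, because T1 does not enter them.

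**The case against.** The strongest reply is that this is loose drafting. Both sentences use 'and', section 9.2 is a recruitment summary, and section 6.3.2, which sets assessment timing, already has the better order. That is a fair reason to call the conflict one of natural reading. It does not remove the gap: if 'and' carries no order, the protocol fixes none, and staff following 9.2 would not be departing from it.

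The second reply is that T0 is an ALS-18 score taken before allocation under either description and already sits in the primary model, and that the post hoc comparisons in section 8 are mostly independent t-tests, which at T2 to T4 do not involve T1. This stands, and it limits the harm. What remains is the omnibus test, which pools all five times, and any comparison that starts from T1.

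A reader might infer that the trial's main result carries a type I error of up to 35%. The documents do not support that: the figure belongs to a T1-to-T2 change-score test, which section 8 does not name, and it needs a 0.3 SD reaction for which the documents give no evidence. A reader might also infer that the trial would be left without a usable baseline; T0 provides one.

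**Conclusion.** The two sections need to be reconciled, and the remedy is procedural. If the 9.2 order is followed and the arm is disclosed before T1, one of the five scores in the primary repeated-measures analysis is an unblinded self-rating made after randomisation. Under the assumptions shown, rejection of the omnibus group-by-time test rises from 5% to about 7%, 15% or 31% for shifts of 0.1, 0.2 or 0.3 SD, and T1-referenced contrasts are biased by the shift itself, against a planned effect of 0.6 SD. Between-arm tests at T2 to T4 and changes from T0 are not affected.

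These figures are illustrative. The size of the reaction and the correlation are assumed, and the direction is unknown: a shift the other way would shrink a true difference in T1-referenced change and cost power instead. It is certain that the two sections list the steps in opposite order and that no safeguard is stated. Whether bias would follow depends on which section is followed, when patients are told, and how they react.

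**What to change.** 1. Reword section 9.2 so that T1 comes before allocation, as in section 6.3.2.
2. State in section 6.2 that the research assistant releases the allocation only after the T1 submission is time-stamped in Research Manager. Section 10.2 already describes an audit of study activities in that system.
3. If a T1 is nevertheless submitted after the arm is known, flag it. Add to section 8 a sensitivity analysis that uses T0 as the pre-randomisation reference for change, for all patients in both arms. Replacing T1 only for the late submitters would mix two references and could do so unequally between arms.

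The cost is a sentence in each section and an ordering check, with no extra visit, measure or patient. The downside is a possible short delay in releasing the allocation to patients who submit T1 late. As psychoeducation groups start once every six weeks, T1 reminders should be timed to the group start. The change has to be made before enrolment, because a T1 rated after disclosure cannot be collected again.

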9.3 Compensation for injury

The sponsor/investigator has a liability insurance which is in accordance with article 7 of the WMO.

The sponsor (also) has an insurance which is in accordance with the legal requirements in the Netherlands (Article 7 WMO). This insurance provides cover for damage to research subjects through injury or death caused by the study.

The insurance applies to the damage that becomes apparent during the study or within 4 years after the end of the study.

9.4 Incentives (if applicable)

There is no special incentive, compensation or treatment that subjects will receive through participating in this study. However, participants will be reimbursed for their extra travel costs.

10 ADMINISTRATIVE ASPECTS, MONITORING AND PUBLICATION

10.1 Handling and storage of data and documents

All data are coded by means of number codes. Only the lead researcher has a key of names and participant numbers; the researchers of the research group of the project only get coded data, i.e., data with participant number, not with names. Codes are in chronological order, each subsequent participant is allocated the subsequent number. The participant data will be stored for up to 15 years after the last measurement of the last participant of this study. On the questionnaires used in this study is only the participant number visible, data is stored on a secure server, using Research Manager (which complies with the Dutch AVG, General Data Protection Regulation). Apart from the researchers of this team, inspectors of the national inspection of health (Inspectie Volksgezondheid) have access to the data.

10.2 Monitoring and Quality Assurance

Research manager will be able to provide an audit of all activities in this study, and changes made in the CRF. A delegation log, is made and kept up to date. The sponsor/investigator will submit a summary of the progress of the trial to the accredited METC once a year. Information will be provided on the date of inclusion of the first subject, numbers of subjects included and numbers of subjects that have completed the trial, serious adverse events/ serious adverse reactions, other problems, and amendments. There is no need to provide a monitor plan in paragraph 7.4 is mentioned that in this study a DSMB is not needed, as the interventions consists of either care as usual, or a variation on care as usual.

10.3 Amendments

Amendments are changes made to the research after a favourable opinion by the accredited METC has been given. All amendments will be notified to the METC that gave a favourable opinion.

All substantial amendments will be notified to the METC and to the competent authority.

10.4 Annual progress report

The sponsor/investigator will submit a summary of the progress of the trial to the accredited METC once a year. Information will be provided on the date of inclusion of the first subject, numbers of subjects included and numbers of subjects that have completed the trial, serious adverse events/ serious adverse reactions, other problems, and amendments.

10.5 Temporary halt and (prematurely) end of study report

The investigator/sponsor will notify the accredited METC of the end of the study within a period of 8 weeks. The end of the study is defined as the last patient's last visit.

The sponsor will notify the METC immediately of a temporary halt of the study, including the reason of such an action.

In case the study is ended prematurely, the sponsor will notify the accredited METC within 15 days, including the reasons for the premature termination.

Within one year after the end of the study, the investigator/sponsor will submit a final study report with the results of the study, including any publications/abstracts of the study, to the accredited METC.

10.6 Public disclosure and publication policy

This trial is in the process of being pre-registered at ClinicalTrials.gov. The sponsor and investigator have agreed to full public disclosure of the research data and aim to publish the research data in a relevant journal, conform guidelines of the CCMO.

11. Ethical considerations

11. 1 Benefits and risk assessment:

Risks for patients participating in this study are minimal. This intervention has been successfully tested in a pilot study (Holmes et al., 2016), suggesting this intervention is able to decline mood variability in patients suffering from bipolar disorder, and also is well tolerated and well received by patients. The ImCT is offered without discontinuing care as usual (visits to the psychiatrist monitoring mood stabilizing medication). The same is the case for psychoeducation treatment. Psychoeducation treatment, although applied using a treatment protocol, is in line with psychological interventions offered routinely to BP patients. The extra burden for participants is the weekly questionnaires (20 minutes), and the questionnaires at T0-T4 (45 minutes), as daily monitoring is advised in current guidelines.

Should patients relapse into mania or depression, they will receive standard care as usual. The benefits of participating in this study are also minimal. For participant in the ImCT condition, there might be the added benefit of having an intervention aimed at changing imagery, expected to form a central part of emotion amplification, but these effects above psychoeducation are not yet demonstrated. For participants in the psychoeducation condition the effects are not different from treatment as usual. It is important to note, they have the possibility to receive ImCT after their participation to this study has ended. In the same line, the patients in the ImCT condition have the possibility to receive psychoeducation after this study has ended.

12 References:

References

- Altman, E. A., Hedekker, D., & Peterson, J. L. (1997). The Altman Self-Rating Mania Scale. *Biological Psychiatry*, 42(10), 948-955.
- Association, A. P. (2013). *Diagnostic and statistical manual of mental disorders (5th ed.)*. Washington, DC: Author.
